NCI CTCAE version 4.0 was used for assessing AE severity. AEs are coded using MedDRA version XX.X.

Path to the program code, date and time of output

Data extracted: DD.MM.YYYY

< System organ classes (SOC) and preferred terms (PT) within each SOC should be sorted in descending order of n (%). >

ML39355_STATISTICAL ANALYSIS PLAN_Final 2.0_17 June 2020

Similar to table 3.7.1, the following tables will be constructed (with the corresponding corrections of underlined fragments in the note):

F. Hoffmann-La Roche Ltd
ML39355

Table 3.7.2 Treatment-emergent adverse events during rollover study by maximum severity

Treated set (TS, patients continuing in the rollover study)

Page X of X

F. Hoffmann-La Roche Ltd
ML39355

Table 3.7.3 Treatment-emergent adverse events during whole study period by maximum severity

Treated set (TS)

Page X of X

F. Hoffmann-La Roche Ltd
ML39355

Table 3.8.1 Treatment-emergent adverse events related to the study drug during treatment period by maximum severity

Treated set (TS)

Page X of X

F. Hoffmann-La Roche Ltd
ML39355

Table 3.8.2 Treatment-emergent adverse events related to the study drug during rollover study by maximum severity

Treated set (TS, patients continuing in the rollover study)

Page X of X

F. Hoffmann-La Roche Ltd
ML39355

Table 3.8.3 Treatment-emergent adverse events related to the study drug during whole study period by maximum severity

Treated set (TS)

Page X of X

ML39355_STATISTICAL ANALYSIS PLAN_Final 2.0_17 June 2020

Similar to table 3.3.1, the following tables will be constructed (with the corresponding corrections of underlined fragments in the note):

F. Hoffmann-La Roche Ltd
ML39355

Table 3.9.1 Treatment-emergent adverse events of special interest during treatment period
Treated set (TS)
Page X of X

F. Hoffmann-La Roche Ltd
ML39355

Table 3.9.2 Treatment-emergent adverse events of special interest during rollover study
Treated set (TS, patients continuing in the rollover study)
Page X of X

F. Hoffmann-La Roche Ltd
ML39355

Table 3.9.3 Treatment-emergent adverse events of special interest during whole study period
Treated set (TS)
Page X of X

F. Hoffmann-La Roche Ltd
ML39355

Table 3.10.1 Treatment-emergent adverse events leading to death during treatment period
Treated set (TS)
Page X of X

F. Hoffmann-La Roche Ltd
ML39355

Table 3.10.2 Treatment-emergent adverse events leading to death during rollover study
Treated set (TS, patients continuing in the rollover study)
Page X of X

F. Hoffmann-La Roche Ltd
ML39355

Table 3.10.3 Treatment-emergent adverse events leading to death during whole study period
Treated set (TS)
Page X of X

F. Hoffmann-La Roche Ltd
ML39355

ML39355_STATISTICAL ANALYSIS PLAN_Final 2.0_17 June 2020

Table 3.11.1 Treatment-emergent adverse events leading to discontinuation of study drug during treatment period

Treated set (TS)

Page X of X

F. Hoffmann-La Roche Ltd

ML39355

Table 3.11.2 Treatment-emergent adverse events leading to discontinuation of study drug during rollover study

Treated set (TS, patients continuing in the rollover study)

Page X of X

F. Hoffmann-La Roche Ltd

ML39355

Table 3.11.3 Treatment-emergent adverse events leading to discontinuation of study drug during whole study period

Treated set (TS)

Page X of X

F. Hoffmann-La Roche Ltd

ML39355

Table 3.12.1 Treatment-emergent adverse events related to the study drug and leading to death during treatment period

Treated set (TS)

Page X of X

F. Hoffmann-La Roche Ltd

ML39355

Table 3.12.2 Treatment-emergent adverse events related to the study drug and leading to death during rollover study

Treated set (TS, patients continuing in the rollover study)

Page X of X

F. Hoffmann-La Roche Ltd

ML39355

Table 3.12.3 Treatment-emergent adverse events related to the study drug and leading to death during whole study period

Treated set (TS)

Page X of X

F. Hoffmann-La Roche Ltd

ML39355

Table 3.13.1 Non-serious treatment-emergent adverse events occurred at a frequency of $\geq 5\%$ during treatment period

Treated set (TS)

Page X of X

F. Hoffmann-La Roche Ltd

ML39355_STATISTICAL ANALYSIS PLAN_Final 2.0_17 June 2020

ML39355

Table 3.13.2 Non-serious treatment-emergent adverse events occurred at a frequency of $\geq 5\%$ during rollover study

Treated set (TS, patients continuing in the rollover study)

Page X of X

F. Hoffmann-La Roche Ltd

ML39355

Table 3.13.3 Non-serious treatment-emergent adverse events occurred at a frequency of $\geq 5\%$ during whole study period

Treated set (TS)

Page X of X

ML39355_STATISTICAL ANALYSIS PLAN_Final 2.0_17 June 2020

Table 3.14 Deaths
Treated set (TS)
Page X of X

	Total (N = XX) n (%)
Total number of deaths	XX (XX.X)
Deaths during treatment period	XX (XX.X)
Deaths during rollover study	XX (XX.X)

N: the number of patients in the Treated set (TS). n: the number of patients who died. Percentages are calculated as $(100 \times n/N)$.

Path to the program code, date and time of output

Data extracted: DD.MM.YYYY

ML39355_STATISTICAL ANALYSIS PLAN_Final 2.0_17 June 2020
Pregnancies

F. Hoffmann-La Roche Ltd
 ML39355
Table 3.15 Urine pregnancy test
 Treated set (TS)
 Page X of X

	Total (N = XX) n (%)
Screening	
n'	XX
Done [1]	XX (XX.X)
Negative [2]	XX (XX.X)
Positive [2]	XX (XX.X)
Not Done [1]	XX (XX.X)
Male subject [1]	XX (XX.X)
Female subject with no childbearing potential [1]	XX (XX.X)
Other [1]	XX (XX.X)
Day 1	
n'	XX
Done [1]	XX (XX.X)
Negative [2]	XX (XX.X)
Positive [2]	XX (XX.X)
Not Done [1]	XX (XX.X)
Male subject [1]	XX (XX.X)
Female subject with no childbearing potential [1]	XX (XX.X)
Other [1]	XX (XX.X)
...	
...	...

N: the number of women of childbearing potential in the TS. n' - the number of valid observations.

n: the number of patients within a specific category.

[1] Percentages are based on the corresponding number of valid observations.

[2] Percentages are based on the number of patients for whom the pregnancy test was performed.

Path to the program code, date and time of output

Data extracted: DD.MM.YYYY

<The following Urine pregnancy test assessments will be presented: Screening, Day 1, Week 4, Week 8, Week 12, Week 20, Week 26 Day 2>

ML39355_STATISTICAL ANALYSIS PLAN_Final 2.0_17 June 2020
Laboratory tests

 F. Hoffmann-La Roche Ltd
 ML39355

Table 3.16 Hematology. Descriptive statistics

Treated set (TS)

Page X of X

Parameter: XXXXXXXXXXXXXXXXXXXX, <units>

	Total (N = XX)	Change from the baseline
Screening		
n	XX	
Mean	XX.X	
SD	XX.XX	
Median	XX.X	
Min	XX	
Max	XX	
Day 1		
n	XX	
Mean	XX.X	
SD	XX.XX	
Median	XX.X	
Min	XX	
Max	XX	
Baseline		
n	XX	
Mean	XX.X	
SD	XX.XX	
Median	XX.X	
Min	XX	
Max	XX	
Week 2		
n	XX	XX
Mean	XX.X	XX.X
SD	XX.XX	XX.XX
Median	XX.X	XX.X
Min	XX	XX
Max	XX	XX

ML39355_STATISTICAL ANALYSIS PLAN_Final 2.0_17 June 2020

...

...

...

N: the number of patients in the Treated set (TS).
n: the number of valid measurements.

The baseline value for a variable is defined as the last non-missing value collected before the first study drug administration.
<The following assessments will be presented: Screening, Day 1, Baseline, Week 2, Week 4, Week 8, Week 16, Week 20, Week 26 Day 2, Follow-up visit, Week 39, Week 52>
<The following parameters will be presented: Leukocytes ($10^9/L$), Erythrocytes ($10^{12}/L$), Hemoglobin (g/L), Hematocrit (L/L), Platelets ($10^9/L$), Neutrophils/Leukocytes (%), Eosinophils/Leukocytes (%), Basophils/Leukocytes (%), Monocytes/Leukocytes (%), Lymphocytes/Leukocytes (%).>

Path to the program code, date and time of output

Data extracted: DD.MM.YYYY

ML39355_STATISTICAL ANALYSIS PLAN_Final 2.0_17 June 2020

Similar to table 3.16, the following tables will be constructed:

F. Hoffmann-La Roche Ltd
ML39355

Table 3.17 Blood chemistry. Descriptive statistics

Treated set (TS)

Page X of X

<The following parameters will be presented: Albumin (g/L), Alkaline Phosphatase (U/L), Alanine Aminotransferase (U/L), Aspartate Aminotransferase (U/L), Direct bilirubin (umol/L), Bilirubin (umol/l), Protein (g/L), Cholesterol (mmol/L), Creatine Kinase (U/L), Creatinine (umol/L), Triglycerides (mmol/L), Gamma Glutamyl Transferase (U/L), Glucose (mmol/L), Lactate Dehydrogenase (U/L), Calcium (mmol/L), Phosphate (mmol/L), Magnesium (mmol/L), Potassium (mmol/L), Sodium (mmol/L), Urea nitrogen (mmol/L), Urate (umol/L), Creatinine Clearance (mL/min).>

ML39355_STATISTICAL ANALYSIS PLAN_Final 2.0_17 June 2020

 F. Hoffmann-La Roche Ltd
 ML39355

Table 3.18 Hematology. Shift table

Treated set (TS)

Page X of X

Parameter: XXXXXXXXXXXXXXXXXXXX, <units>

	Baseline			Total
	Low	Normal	High	
Baseline				
Low				XX (XX.X)
Normal				XX (XX.X)
High				XX (XX.X)
Total				XX (100)
Week 2				
Low	XX (XX.X)	XX (XX.X)	XX (XX.X)	XX (XX.X)
Normal	XX (XX.X)	XX (XX.X)	XX (XX.X)	XX (XX.X)
High	XX (XX.X)	XX (XX.X)	XX (XX.X)	XX (XX.X)
Total	XX (XX.X)	XX (XX.X)	XX (XX.X)	XX (100)
Week 4				
Low	XX (XX.X)	XX (XX.X)	XX (XX.X)	XX (XX.X)
Normal	XX (XX.X)	XX (XX.X)	XX (XX.X)	XX (XX.X)
High	XX (XX.X)	XX (XX.X)	XX (XX.X)	XX (XX.X)
Total	XX (XX.X)	XX (XX.X)	XX (XX.X)	XX (100)
...				
...

The baseline value for a variable is defined as the last non-missing value collected before the first study drug administration. Percentages are based on the number of patients with a non-missing assessment at the corresponding time point and at baseline.

<The following assessments will be presented: Baseline, Week 2, Week 4, Week 8, Week 16, Week 20, Week 26 Day 2, Follow-up visit, Week 39, Week 52>

Path to the program code, date and time of output

Data extracted: DD.MM.YYYY

ML39355_STATISTICAL ANALYSIS PLAN_Final 2.0_17 June 2020

Similar to table 3.18, the following tables will be constructed:

F. Hoffmann-La Roche Ltd
ML39355
Table 3.19 Blood chemistry. Shift table
Treated set (TS)
Page X of X

ML39355_STATISTICAL ANALYSIS PLAN_Final 2.0_17 June 2020

 F. Hoffmann-La Roche Ltd
 ML39355

Table 3.20 Hematology. Out of range. Frequency table

Treated set (TS)

Page X of X

Parameter: XXXXXXXXXXXXXXX, <units>

	Total (N = XX) n (%)
Screening	
n'	XX
Normal	XX (XX.X)
Out of Range NCS	XX (XX.X)
Out of Range CS	XX (XX.X)
Day 1	
n'	XX
Normal	XX (XX.X)
Out of Range NCS	XX (XX.X)
Out of Range CS	XX (XX.X)
Baseline	
n'	XX
Normal	XX (XX.X)
Out of Range NCS	XX (XX.X)
Out of Range CS	XX (XX.X)
Week 2	
n'	XX
Normal	XX (XX.X)
Out of Range NCS	XX (XX.X)
Out of Range CS	XX (XX.X)
...	...
...	...

N: the number of patients in the Treated set (TS). n' - the number of valid observations.

n: the number of patients within a specific category. Percentages are based on the corresponding number of valid observations.

<The following assessments will be presented: Screening, Day 1, Baseline, Week 2, Week 4, Week 8, Week 16, Week 20, Week 26 Day 2, Follow-up visit, Week 39, Week 52>

ML39355_STATISTICAL ANALYSIS PLAN_Final 2.0_17 June 2020

Similar to table 3.20, the following tables will be constructed:

F. Hoffmann-La Roche Ltd
ML39355

Table 3.21 Blood chemistry. Out of range. Frequency table

Treated set (TS)

Page X of X

ML39355_STATISTICAL ANALYSIS PLAN_Final 2.0_17 June 2020
Vital signs

 F. Hoffmann-La Roche Ltd
 ML39355

Table 3.22 Vital signs. Descriptive statistics

Treated set (TS)

Page X of X

Parameter: XXXXXXXXXXXXXXXX, <units>

	Total (N = XX)	Change from the baseline
Screening		
n	XX	
Mean	XX.X	
SD	XX.XX	
Median	XX.X	
Min	XX	
Max	XX	
Day 1		
n	XX	
Mean	XX.X	
SD	XX.XX	
Median	XX.X	
Min	XX	
Max	XX	
Baseline		
n	XX	
Mean	XX.X	
SD	XX.XX	
Median	XX.X	
Min	XX	
Max	XX	
Week 2		
n	XX	XX
Mean	XX.X	XX.X
SD	XX.XX	XX.XX
Median	XX.X	XX.X
Min	XX	XX
Max	XX	XX

ML39355_STATISTICAL ANALYSIS PLAN_Final 2.0_17 June 2020

...

...

...

N: the number of patients in the Treated set (TS).
n: the number of valid measurements.

The baseline value for a variable is defined as the last non-missing value collected before the first study drug administration.

Path to the program code, date and time of output

Data extracted: DD.MM.YYYY

<Report all parameters: Systolic blood pressure, mm Hg/ Diastolic blood pressure, mm Hg/ Pulse rate, beats/minute/ Respiratory rate, breaths/minute/
Axillary temperature, C>
<The following assessments will be presented: Screening, Day 1, Baseline, Week 2, Week 4, Week 8, Week 16, Week 20, Week 26 Day 1, Week 26 Day 2,
Follow-up visit, Week 39, Week 52>

ML39355_STATISTICAL ANALYSIS PLAN_Final 2.0_17 June 2020

 F. Hoffmann-La Roche Ltd
 ML39355

Table 3.23 Vital signs. Out of range. Frequency table

Treated set (TS)

Page X of X

Parameter: XXXXXXXXXXXXXXX, <units>

	Total (N = XX) n (%)
Screening	
n'	XX
Normal	XX (XX.X)
Out of Range NCS	XX (XX.X)
Out of Range CS	XX (XX.X)
Day 1	
n'	XX
Normal	XX (XX.X)
Out of Range NCS	XX (XX.X)
Out of Range CS	XX (XX.X)
Baseline	
n'	XX
Normal	XX (XX.X)
Out of Range NCS	XX (XX.X)
Out of Range CS	XX (XX.X)
Week 2	
n'	XX
Normal	XX (XX.X)
Out of Range NCS	XX (XX.X)
Out of Range CS	XX (XX.X)
...	
...	...

N: the number of patients in the Treated set (TS). n' - the number of valid observations.

n: the number of patients within a specific category. Percentages are based on the corresponding number of valid observations.

ML39355_STATISTICAL ANALYSIS PLAN_Final 2.0_17 June 2020

Path to the program code, date and time of output

Data extracted: DD.MM.YYYY

<Report all parameters: Systolic blood pressure, mm Hg/ Diastolic blood pressure, mm Hg/ Pulse rate, beats/minute/ Respiratory rate, breaths/minute/
Axillary temperature, C>
<The following assessments will be presented: Screening, Day 1, Baseline, Week 2, Week 4, Week 8, Week 16, Week 20, Week 26 Day 1, Week 26 Day 2,
Follow-up visit, Week 39, Week 52>

ML39355_STATISTICAL ANALYSIS PLAN_Final 2.0_17 June 2020
Weight

 F. Hoffmann-La Roche Ltd
 ML39355

Table 3.24 Weight. Descriptive statistics

Treated set (TS)

Page X of X

Parameter: Weight, kg

	Total (N = XX)	Change from the baseline
Screening		
n	XX	
Mean	XX.XX	
SD	XX.XXX	
Median	XX.XX	
Min	XX.X	
Max	XX.X	
Day 1		
n	XX	
Mean	XX.XX	
SD	XX.XXX	
Median	XX.XX	
Min	XX.X	
Max	XX.X	
Baseline		
n	XX	
Mean	XX.XX	
SD	XX.XXX	
Median	XX.XX	
Min	XX.X	
Max	XX.X	
Week 2		
n	XX	XX
Mean	XX.XX	XX.XX
SD	XX.XXX	XX.XXX
Median	XX.XX	XX.XX
Min	XX.X	XX.X
Max	XX.X	XX.X

ML39355_STATISTICAL ANALYSIS PLAN_Final 2.0_17 June 2020

...

...

...

N: the number of patients in the Treated set (TS).
n: the number of valid measurements.

The baseline value for a variable is defined as the last non-missing value collected before the first study drug administration.

Path to the program code, date and time of output

Data extracted: DD.MM.YYYY

<The following assessments will be presented: Screening, Day 1, Baseline, Week 2, Week 4, Week 8, Week 16, Week 20, Week 26 Day 2, Follow-up visit>

ML39355_STATISTICAL ANALYSIS PLAN_Final 2.0_17 June 2020
ECG

 F. Hoffmann-La Roche Ltd
 ML39355

Table 3.25 ECG. Descriptive statistics

Treated set (TS)

Page X of X

Parameter: XXXXXXXXXXXXXXXX, <units>

	Total (N = XX)	Change from the baseline
Screening		
n	XX	
Mean	XX.X	
SD	XX.XX	
Median	XX.X	
Min	XX	
Max	XX	
Day 1		
n	XX	
Mean	XX.X	
SD	XX.XX	
Median	XX.X	
Min	XX	
Max	XX	
Baseline		
n	XX	
Mean	XX.X	
SD	XX.XX	
Median	XX.X	
Min	XX	
Max	XX	
Week 4		
n	XX	XX
Mean	XX.X	XX.X
SD	XX.XX	XX.XX
Median	XX.X	XX.X
Min	XX	XX
Max	XX	XX

ML39355_STATISTICAL ANALYSIS PLAN_Final 2.0_17 June 2020

...

...

...

N: the number of patients in the Treated set (TS).
n: the number of valid measurements.

The baseline value for a variable is defined as the last non-missing value collected before the first study drug administration.

Path to the program code, date and time of output

Data extracted: DD.MM.YYYY

<Report all parameters: Heart rate, beats/min/ QT interval, ms/ QTC-F interval, ms>

<The following assessments will be presented: Screening, Day 1, Baseline, Week 4, Week 8, Week 26 Day 2, Week 52>

ML39355_STATISTICAL ANALYSIS PLAN_Final 2.0_17 June 2020

 F. Hoffmann-La Roche Ltd
 ML39355

Table 3.26 ECG. Out of range and General assessment. Frequency table

 Treated set (TS)
 Page X of X

Parameter: XXXXXXXXXXXXXXXXX

	Total (N = XX) n (%)
Screening	
n'	XX
Normal	XX (XX.X)
Abnormal NCS	XX (XX.X)
Abnormal CS	XX (XX.X)
Day 1	
n'	XX
Normal	XX (XX.X)
Abnormal NCS	XX (XX.X)
Abnormal CS	XX (XX.X)
Baseline	
n'	XX
Normal	XX (XX.X)
Abnormal NCS	XX (XX.X)
Abnormal CS	XX (XX.X)
Week4	
n'	XX
Normal	XX (XX.X)
Abnormal NCS	XX (XX.X)
Abnormal CS	XX (XX.X)
...	
...	...

N: the number of patients in the Treated set (TS). n' - the number of valid observations.

n: the number of patients within a specific category. Percentages are based on the corresponding number of valid observations.

ML39355_STATISTICAL ANALYSIS PLAN_Final 2.0_17 June 2020

Path to the program code, date and time of output

Data extracted: DD.MM.YYYY

<Report all parameters: General assessment/ Heart rate, beats/min/ QT interval, ms/ QTC-F interval, ms>

<The following assessments will be presented: Screening, Day 1, Baseline, Week 4, Week 8, Week 26 Day 2, Week 52>

ML39355_STATISTICAL ANALYSIS PLAN_Final 2.0_17 June 2020
Physical examinations

 F. Hoffmann-La Roche Ltd
 ML39355

Table 3.27 Physical examinations. Frequency table

Treated set (TS)

Page X of X

Body system: XXXXXXXXXXXXX

	Total (N = XX) n (%)
Screening	
n'	XX
Normal	XX (XX.X)
Abnormal NCS	XX (XX.X)
Abnormal CS	XX (XX.X)
Day 1	
n'	XX
Normal	XX (XX.X)
Abnormal NCS	XX (XX.X)
Abnormal CS	XX (XX.X)
Baseline	
n'	XX
Normal	XX (XX.X)
Abnormal NCS	XX (XX.X)
Abnormal CS	XX (XX.X)
Week 2	
n'	XX
Normal	XX (XX.X)
Abnormal NCS	XX (XX.X)
Abnormal CS	XX (XX.X)
...	
...	...

N: the number of patients in the Treated set (TS). n' - the number of valid observations.

n: the number of patients within a specific category. Percentages are based on the corresponding number of valid observations.

ML39355_STATISTICAL ANALYSIS PLAN_Final 2.0_17 June 2020

Path to the program code, date and time of output

Data extracted: DD.MM.YYYY

<The following assessments will be presented: Screening, Day 1, Baseline, Week 2, Week 4, Week 8, Week 16, Week 20, Week 26 Day 1, Week 26 Day 2, Follow-up visit, Week 39, Week 52>

ML39355_STATISTICAL ANALYSIS PLAN_Final 2.0_16 June 2020

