6.3. Missing Data⁴

For missing FVC data imputation, patients will be classified into different patterns depending on the availability of data:

Patients with a 26 week FVC value:

1. those who received study drug until 26 weeks (completed the treatment period);
2. those who prematurely discontinued study drug, but who were followed up until Week 26.

Patients without a 26 Week FVC value:

3. those who were alive at 26 weeks;
4. those who died before 26 weeks.

Missing data at other visits before Week 26 (primary outcome variable) will not be imputed.

The following imputation methods including sensitivity analyses will be applied for patients with pattern 3 - 4:

Assuming that deaths of the patients (pattern 4) is likely to be related to worsening of IPF, these unobserved FVC values should be lower than those in patients who did not die prior to Week 26.

Methods for handling missing data due to death will include the following:

- Replacement with the worst possible value (FVC= 0 mL or 0%) (Primary analysis).
- Replacement with worst observed averaged FVC value at week 26 (Sensitivity analysis).

⁴ This section is based on the section 6.2 “Summaries of conduct of study” of clinical study Protocol.

ML39355_STATISTICAL ANALYSIS PLAN_Final 2.0_17 June 2020

- Replacement with an intermediate value (FVC =1500 mL or 50%) (Sensitivity analysis).

Missing data due to reasons other than death (e.g., missing visits, early withdrawal from the study, including missing values due to lung transplantations) (pattern 3) will be replaced with imputed values based on the average measurements for “similar” patients at that time point. Similar patients are those without missing data before that time point and whose data have the smallest sum of squared deviations (SSD) from that patient for all visits prior to the one with the missing data. Missing data due to lung transplant will be imputed using the SSD method even if the patient dies after lung transplant.

The procedure referred to as the sum of squared deviations (SSD) is outlined as follows:

Step 1: For post-Baseline missing value to be imputed at a visit (Visit week 26) for a particular patient (Patient A), a set of all patients without any missing values for visits from Baseline up to Visit week 26 as Patient A will be selected.

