6.6. Multiple Testing

No adjustment for multiplicity is planned.

7. Summary of Study Data

Demographic and other baseline characteristics, efficacy and safety data will be summarized by time point of assessment and listed.

Default Summary Statistics

The default summary statistics for quantitative and ordinal variables will be the number of observations (n), mean, standard deviation (SD), median, minimum (Min) and maximum (Max).

Default Frequency Tabulations

For qualitative variables, the number and percentage (n, %) of patients with non-missing data per category and total number of patients with non-missing data where applicable (n') will be the default summary presentation.

For AEs and medical history, however, the denominator for the percentage calculation will be the number of patients at risk. A patient will be considered at risk if the patient is in the Treated set.

⁵ This section is based on the section 6.6 “Interim analysis” of clinical study Protocol.

ML39355_STATISTICAL ANALYSIS PLAN_Final 2.0_17 June 2020

The number of decimals for each descriptive statistic will be determined by the following rules:

- mean, median: +1 decimal symbols compared to the analysed variable values;
- standard deviation: +2 decimal symbols compared to the analysed variable values;
- minimum and maximum values: the same as for the analysed variable values;
- percentages will be rounded to one decimal symbol;
- confidence intervals will be presented with accuracy of the estimated value.

The maximum number of decimal places in the statistical report is four. If some descriptive statistic has more than four decimal places after above mentioned rules application, this value will be rounded to four decimal places.

Statistical Tests and Common Calculations

Unless otherwise specified in the description of the analyses, the following arrangements will be applied:

- 95% two-sided confidence intervals (CI);
- [if appropriate] CIs for mean values will be calculated based on normal distribution (SAS procedure UNIVARIATE with CIBASIC option);
- [if appropriate] CIs for proportions will be computed using the exact (Clopper-Pearson) method.
- Type I error values (p-values) will be rounded to four decimal symbols.

For descriptive statistics and analysis, the following rules will be applied:

- “<XX” results (e.g. below the limit of quantification, BLQ) will be replaced by the “XX/2” values;

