8.2. Secondary Efficacy Analyses

eCRF form: “6-Minute Walk Test”, “BORG SCALE”, “EUROPEAN QUALITY OF LIFE 5-DIMENSION 5-LEVEL QUESTIONNAIRE”.

Change in 6MWT distance from Baseline to Week 26

Baseline 6MWT distance will be the average of the measurements recorded at the Screening and Day 1 visits. The 6MWT distance at Week 26 will be defined as the average of the 6MWT distance recorded on two separate days at Week 26. Data will be analyzed using standard descriptive statistics for continuous variables and 95% CI for the means and mean absolute changes.

The distribution (number and percentage) of 6MWT distance across three categories of change from Baseline (Decline of ≥ 50 m or death before Week 26; Decline of < 50 m to 0 m (exclusively), Improvement of ≥ 0 m) will be provided in frequency table.

Additionally, the absolute change in 6MWT from Baseline at Week 39 (optional) and Week 52 (optional) will be summarized in table with standard descriptive statistics for continuous variables and 95% CI for the mean.

Borg scale results will be presented descriptively by visit of assessment. Borg scale results (as a continuous variable) will be presented for both pre-test and post-test by visit of assessment and change from baseline (the average of the measurements recorded at the Screening and Day 1 visits) at post-baseline visits for pre-test assessments only.

The Borg scale results at Week 26 will be defined as the average of the Borg scale results recorded on two separate days at Week 26. If at baseline and/or at Week 26 for 6MWT distance or Borg scale either value is missing, the non-missing value will be used.

Descriptive analysis for 6MWT distance and Borg scale results will be repeated excluding assessments outside of visit window.

Change from Baseline to Week 26 in patients' quality of life as measured with EQ-5D-5L

- Cross tabulation for each of five dimensions (Mobility, Self-Care, Usual Activities, Pain / Discomfort, Anxiety / Depression) by response and study week.

ML39355_STATISTICAL ANALYSIS PLAN_Final 2.0_17 June 2020

- VAS score, including absolute changes from baseline, will be summarized with descriptive statistics by study week.
- EQ-5D-5L index score using the UK value set, including absolute changes from baseline, will be summarized with descriptive statistics by study week.

Descriptive analysis will be repeated excluding assessments outside of visit window.

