Mean [95% CI]	XX.X [XX.X - XX.X]	XX.X [XX.X - XX.X]
SD	XX.XX	XX.XX
Median	XX.X	XX.X
Min	XX	XX
Max	XX	XX
Week 26, Pattern 1		
n	XX	XX
Mean [95% CI]	XX.X [XX.X - XX.X]	XX.X [XX.X - XX.X]

ML39355_STATISTICAL ANALYSIS PLAN_Final 2.0_17 June 2020

SD	XX.XX	XX.XX
Median	XX.X	XX.X
Min	XX	XX
Max	XX	XX
Week 26, Pattern 2		
n	XX	XX
Mean [95% CI]	XX.X [XX.X - XX.X]	XX.X [XX.X - XX.X]
SD	XX.XX	XX.XX
Median	XX.X	XX.X
Min	XX	XX
Max	XX	XX

N: the number of patients in the CCS. n: the number of valid measurements.

Baseline FVC is the average of the pre-bronchodilator FVC measured at the Screening and Day 1 visits. The FVC at Week 26 is the average of the FVC measured on two separate days at Week 26.

Pattern 1: Patients who received study drug until 26 weeks;

Pattern 2: Patients who prematurely discontinued study drug, but who were followed up until Week 26.

Path to the program code, date and time of output

Data extracted: DD.MM.YYYY

ML39355_STATISTICAL ANALYSIS PLAN_Final 2.0_17 June 2020
Secondary Efficacy Endpoint
6-Minute Walk Test

F. Hoffmann-La Roche Ltd
 ML39355
Table 2.5 6-Minute Walk Test
 Full analysis set (FAS)
 Page X of X

	Total (N = XX)	Change from the baseline
6-Minute Walk Test, m		
Screening		
n	XX	
Mean [95% CI]	XX.X [XX.X - XX.X]	
SD	XX.XX	
Median	XX.X	
Min	XX	
Max	XX	
Day 1		
n	XX	
Mean [95% CI]	XX.X [XX.X - XX.X]	
SD	XX.XX	
Median	XX.X	
Min	XX	
Max	XX	
Baseline		
n	XX	
Mean [95% CI]	XX.X [XX.X - XX.X]	
SD	XX.XX	
Median	XX.X	
Min	XX	
Max	XX	
Week 12		
n	XX	XX
Mean [95% CI]	XX.X [XX.X - XX.X]	XX.X [XX.X - XX.X]
SD	XX.XX	XX.XX
Median	XX.X	XX.X
Min	XX	XX

ML39355_STATISTICAL ANALYSIS PLAN_Final 2.0_17 June 2020

Max	XX	XX
Week 12*		
n	XX	XX
Mean [95% CI]	XX.X [XX.X - XX.X]	XX.X [XX.X - XX.X]
SD	XX.XX	XX.XX
Median	XX.X	XX.X
Min	XX	XX
...		
Week 52		
n	XX	XX
Mean [95% CI]	XX.X [XX.X - XX.X]	XX.X [XX.X - XX.X]
SD	XX.XX	XX.XX
Median	XX.X	XX.X
Min	XX	XX
Max	XX	XX
Week 52*		
n	XX	XX
Mean [95% CI]	XX.X [XX.X - XX.X]	XX.X [XX.X - XX.X]
SD	XX.XX	XX.XX
Median	XX.X	XX.X
Min	XX	XX

N: the number of patients in the FAS.

n: the number of valid measurements.

Baseline 6MWT distance is the average of the measurements measured at the Screening and Day 1 visits. The 6MWT distance at Week 26 is defined as the average of the 6MWT distance measured on two separate days at Week 26.

*: Values assessed within the corresponding visit window.

Path to the program code, date and time of output

Data extracted: DD.MM.YYYY

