<The following assessments will be presented: Screening, Day 1, Baseline, Week 12, Week 26 Day 1, Week 26 Day 2, Week 26, Week 39, Week 52>

<Values within the visit window will also be presented descriptively for the following assessments: Week 12*, Week 26 Day 1*, Week 26 Day 2*, Week 26*, Week 39*, Week 52*>

ML39355_STATISTICAL ANALYSIS PLAN_Final 2.0_17 June 2020

 F. Hoffmann-La Roche Ltd
 ML39355

Table 2.6 Change in 6MWT distance at Week 26 by category

 Full analysis set (FAS)
 Page X of X

	Total (N = XX)
n'	n (%)
	XX
Patients with decline of ≥ 50 m from Baseline or death before Week 26	XX (XX.X)
Patients with decline of < 50 m to 0 m from Baseline	XX (XX.X)
Patients with improvement of ≥ 0 m from Baseline	XX (XX.X)

N: the number of patients in the Full analysis set (FAS). n' - the number of valid observations.

n: the number of patients within a specific category. Percentages are based on the corresponding number of valid observations.

Path to the program code, date and time of output

Data extracted: DD.MM.YYYY

ML39355_STATISTICAL ANALYSIS PLAN_Final 2.0_17 June 2020

 F. Hoffmann-La Roche Ltd
 ML39355

Table 2.7 Borg scale
 Full analysis set (FAS)
 Page X of X

	Total (N = XX)	Change Pre-test from Baseline Pre-test	Change Post-test from Pre-test
Borg scale			
Screening Pre-test			
n	XX		
Mean [95% CI]	XX.XX [XX.XX - XX.XX]		
SD	XX.XXX		
Median	XX.XX		
Min	XX.X		
Max	XX.X		
Screening Post-test			
n	XX		XX
Mean [95% CI]	XX.XX [XX.XX - XX.XX]		XX.XX [XX.XX - XX.XX]
SD	XX.XXX		XX.XXX
Median	XX.XX		XX.XX
Min	XX.X		XX.X
Max	XX.X		XX.X
Day 1 Pre-test			
n	XX		
Mean [95% CI]	XX.XX [XX.XX - XX.XX]		
SD	XX.XXX		
Median	XX.XX		
Min	XX.X		
Max	XX.X		
Day 1 Post-test			
n	XX		XX
Mean [95% CI]	XX.XX [XX.XX - XX.XX]		XX.XX [XX.XX - XX.XX]
SD	XX.XXX		XX.XXX
Median	XX.XX		XX.XX
Min	XX.X		XX.X
Max	XX.X		XX.X
...			
...			

ML39355_STATISTICAL ANALYSIS PLAN_Final 2.0_17 June 2020

Week 26 Day 1 Pre-test			
n	XX	XX	
Mean [95% CI]	XX.XX [XX.XX - XX.XX]	XX.XX [XX.XX - XX.XX]	
SD	XX.XXX	XX.XXX	
Median	XX.XX	XX.XX	
Min	XX.X	XX.X	
Max	XX.X	XX.X	
Week 26 Day 1 Post-test			
n	XX		XX
Mean [95% CI]	XX.XX [XX.XX - XX.XX]		XX.XX [XX.XX - XX.XX]
SD	XX.XXX		XX.XXX
Median	XX.XX		XX.XX
Min	XX.X		XX.X
Max	XX.X		XX.X
Week 26* Day 1 Pre-test			
n	XX	XX	
Mean [95% CI]	XX.XX [XX.XX - XX.XX]	XX.XX [XX.XX - XX.XX]	
SD	XX.XXX	XX.XXX	
Median	XX.XX	XX.XX	
Min	XX.X	XX.X	
Max	XX.X	XX.X	
Week 26* Day 1 Post-test			
n	XX		XX
Mean [95% CI]	XX.XX [XX.XX - XX.XX]		XX.XX [XX.XX - XX.XX]

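### The Week 26 6MWT mean change leaves out deaths and survivors without a walk, has no missing-data sensitivity analysis, and Table 2.6 does not say whether deaths are in its denominator

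*SAP*

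**What the plan says.** **Week 26 walking distance.** SAP Section 8.2 states: "The 6MWT distance at Week 26 will be defined as the average of the 6MWT distance recorded on two separate days at Week 26". The only provision for missing values is: "If at baseline and/or at Week 26 for 6MWT distance or Borg scale either value is missing, the non-missing value will be used". Nothing covers a patient with neither Week 26 walk, or one who died. The footnote to Table 2.5, which reports the mean change, reads "n: the number of valid measurements".

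**Imputation.** SAP Section 6.3 opens its rules with "For missing FVC data imputation, patients will be classified into different patterns depending on the availability of data". Those rules (worst value for death, SSD matching for other reasons, LOCF as an alternative) concern FVC, as they do in Protocol Section 6.2. SAP Section 8.1 then sets FVC to 0 for deaths in the primary analysis and lists six alternative imputation schemes.

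**Categories.** SAP Section 8.2 defines the worst 6MWT category as "Decline of ≥ 50 m or death before Week 26", and Table 2.6 repeats it as "Patients with decline of ≥ 50 m from Baseline or death before Week 26". The Table 2.6 footnote says: "Percentages are based on the corresponding number of valid observations". SAP Section 7 (Default Frequency Tabulations) describes n' as the "total number of patients with non-missing data where applicable".

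**The concern.** Two things are at stake.

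First, the trial has one arm, so the mean 6MWT change and its confidence interval are the main continuous result for functional capacity. If the patients who fare worst have no Week 26 walk, that mean describes a selected group and tends to look better than the cohort did. SAP Section 6.3 makes this argument for FVC: it presumes that deaths probably reflect worsening IPF, so the unseen values would be lower. The plan acts on it for FVC and not for 6MWT.

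Second, a composite category that includes death needs a denominator that says how deaths are counted. The FVC counterpart, Table 2.3, carries the same footnote, but there a death receives an FVC value in the primary analysis and in sensitivity analyses 1 to 6, so the footnote works. In Table 2.6 no value is assigned, and two programmers could produce different percentages from the same data.

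**Working it through.** No figure in the plan is disputed. The only planning figure used is the sample size, which reproduces: 0.601 × 0.399 × (1.96/0.125)² = 58.96, taken as 60.

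**Step 1: who is in the Week 26 mean.** Section 6.3 does not reach 6MWT, and Section 8.2 only substitutes one walk for the other. A patient with no Week 26 walk, dead or alive, therefore has no value, and n in Table 2.5 excludes that patient. The planned repeat of the 6MWT summary removes out-of-window assessments and adds nobody. SAP Section 8 also mentions the Complete case set, but the 6MWT tables are specified for the FAS, and a complete-case repeat could not bring deaths back.

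**Step 2: an assumed range for deaths.** The documents give no expected number. Protocol Appendix 6 gives one-year mortality of 5.6%, 16.2% and 39.2% for GAP stages I, II and III. At constant hazard, 26-week mortality is 1 − (1 − p)^0.5, that is 2.8%, 8.5% and 22.0%, or about 2, 5 and 13 of 60. The top value is extreme: it puts every patient in stage III, while Protocol Section 4.1.2 excludes patients judged to have less than 12 months to live.

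**Step 3: effect on the mean.** Let w patients have a walk with mean change x, and let d have died, with mean baseline distance B. Scoring death as 0 m gives each death a change of −B. The difference from the observed-case mean is −d(B + x)/(w + d). Assume w + d = 60 and x = 0, so the difference is −dB/60. Baseline distance is not given beyond the 100 m screening minimum, so the shift is shown per 100 m of B:

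| Deaths | Shift per 100 m of baseline distance |
|---|---|
| 2 | −3.3 m |
| 5 | −8.3 m |
| 13 | −21.7 m |

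**Step 4: three readings of Table 2.6.** Assume 60 in the FAS, no survivor without a walk, and about a 20/40/40 split among walkers. Reading A counts deaths in the row but not in n'. Reading B leaves them out of both. Reading C counts them in both. The total under A is 100 × 60/(60 − d).

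| Deaths | Walkers by category | A: worst row (total) | B: worst row | C: worst row |
|---|---|---|---|---|
| 2 | 12, 23, 23 | 14/58 = 24.1% (103.4%) | 12/58 = 20.7% | 14/60 = 23.3% |
| 5 | 11, 22, 22 | 16/55 = 29.1% (109.1%) | 11/55 = 20.0% | 16/60 = 26.7% |
| 13 | 9, 19, 19 | 22/47 = 46.8% (127.7%) | 9/47 = 19.1% | 22/60 = 36.7% |

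B and C total 100%, but B omits the deaths that the row label names.

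**Step 5: limit under every reading.** The FAS needs at least one post-baseline efficacy assessment, and the first scheduled one is at Week 12. A patient who dies before any such assessment is outside the FAS and outside both tables whatever n' means. The death counts above, taken on all 60, therefore overstate those that could enter.

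**The case against.** A reader might infer that Table 2.6 as specified must either total more than 100% or lose its deaths. The documents do not support that. The footnote refers to valid observations, not to valid walks, and Section 7 ties n' to non-missing data. A patient who died has a known category in this table, so counting that patient in n' is allowed, and the table is then right. Dropping deaths would contradict the row label. If deaths are counted in the row, a denominator of walks alone makes the result look worse, not better. This objection stands, and it reduces the Table 2.6 point to a clarification. The row label does not settle the matter by itself, however: Table 2.3 uses the same label for sensitivity analyses 8 and 9 on the Complete case set, which admits only patients with Week 26 FVC data.

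A reader might also call the 6MWT mean a survivors-only result. It is narrower: survivors without a Week 26 walk are missing too.

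On the mean, the case for the plan is that 6MWT is descriptive, with no test, success criterion or testing hierarchy, that the observed-case basis is visible from n, and that death enters the endpoint through the category table. All of that is true. It shows that the planned summary is legitimate, but not that it should be the only one. It can also be said that 0 m for death lets a few deaths dominate the mean, which Step 3 confirms, and that SSD would have only baseline and Week 12 to match on. The second limit applies equally to FVC, where the plan accepts it.

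**Conclusion.** The concern holds for the continuous result. Followed as written, the plan's only Week 26 6MWT means rest on observed walks, with no analysis of what the missing patients might do to them. The direction of bias is conditional: it favours benefit if deaths, and missing walks among survivors, reflect worsening disease. The SAP presumes this for deaths when handling FVC; carrying it over to walking is an inference. The size is unknown. The shifts of about 3 to 22 m per 100 m of baseline distance rest on assumed deaths, constant hazard, a mean change of zero among walkers and no missing survivors.

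For Table 2.6 the finding is that the denominator is undefined, not that the table is wrong. With 5 assumed deaths the worst-category rate could be 29.1%, 20.0% or 26.7% depending on the reading, and only the last is coherent. These percentages are illustrations on assumed counts.

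The primary FVC analysis is not affected. The change is worth making before database soft lock, up to which SAP Section 2 allows revisions.

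**What to change.** 1. **Table 2.5.** Keep the Week 26 row and label it observed cases. Add one supportive row that applies the primary FVC missing-data rules to 6MWT: 0 m for death, SSD matching for other missing values. The same visits supply the data (Screening, Day 1 and Week 12). Note beside the row that a few deaths can strongly influence this mean.
2. **Table 2.6.** State in the footnote that n' is the number of FAS patients with a Week 26 6MWT value plus FAS patients who died before Week 26. Show deaths and survivors without a value as separate counts.

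The cost is one extra row, two counts and a footnote, with no new data collection. The supportive mean may look less favourable than the observed-case mean. Neither change reaches deaths before any post-baseline efficacy assessment, which stay outside the FAS; the text should say so.
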